9.5 Interim analyses

No interim analyses are planned in this trial.

9.5.1 Data Safety Monitoring Board (DSMB)

Details regarding DSMB are provided in Section [8.4.6](#).

11. SUPPORTING DOCUMENTATION AND OPERATIONAL CONSIDERATIONS

Appendix A Regulatory, ethical and study oversight considerations

A 1 Regulatory and ethical considerations

This study will be conducted in accordance with the protocol and with the following:

- Consensus ethical principles derived from international guidelines including the Declaration of Helsinki and Council for International Organizations of Medical Sciences (CIOMS) International Ethical Guidelines
- Applicable ICH Good Clinical Practice (GCP) Guidelines
- Applicable laws and regulations

The protocol, protocol amendments, ICF, Investigator Brochure, and other relevant documents (e.g., advertisements) must be submitted to an IRB/IEC by the investigator and reviewed and approved by the IRB/IEC before the study is initiated.

Any amendments to the protocol will require IRB/IEC approval before implementation of changes made to the study design, except for changes necessary to eliminate an immediate hazard to study subjects.

The investigator will be responsible for the following:

- Providing written summaries of the status of the study to the IRB/IEC annually or more frequently in accordance with the requirements, policies, and procedures established by the IRB/IEC
- Notifying the IRB/IEC of SAEs or other significant safety findings as required by IRB/IEC procedures
- Providing oversight of the conduct of the study at the site and adherence to requirements of 21 CFR, ICH guidelines, the IRB/IEC, European regulation 536/2014 for clinical studies (if applicable), and all other applicable local regulations

The study will be performed in accordance with the AstraZeneca policy on Bioethics and Human Biological Samples.

A 2 Financial disclosure

Investigators and sub-investigators will provide the sponsor with sufficient, accurate financial information as requested to allow the sponsor to submit complete and accurate financial

certification or disclosure statements to the appropriate regulatory authorities. Investigators are responsible for providing information on financial interests during the course of the study and for 1 year after completion of the study.

A 3 Informed consent process

The investigator or his/her representative will explain the nature of the study to the subject or his/her legally authorized representative and answer all questions regarding the study.

Subjects must be informed that their participation is voluntary. Subjects or their legally authorized representative will be required to sign a statement of informed consent that meets the requirements of 21 CFR 50, local regulations, ICH guidelines, Health Insurance Portability and Accountability Act (HIPAA) requirements, where applicable, and the IRB/IEC or study centre.

The medical record must include a statement that written informed consent was obtained before the subject was enrolled in the study and the date the written consent was obtained. The authorized person obtaining the informed consent must also sign the ICF.

Subjects must be re-consented to the most current version of the ICF(s) during their participation in the study.

A copy of the ICF(s) must be provided to the subject or the subject's legally authorized representative.

If subject declines to participate in any voluntary exploratory genetic research component of the study, there will be no penalty or loss of benefit to the subject and he/she will not be excluded from other aspects of the study.

Subjects who are rescreened are required to sign a new ICF.

The ICF will contain a separate section that addresses the use of remaining mandatory samples for optional exploratory research. The investigator or authorized designee will explain to each subject the objectives of the exploratory research. Subjects will be told that they are free to refuse to participate and may withdraw their consent at any time and for any reason during the storage period. The subject will give a separate agreement to allow any remaining specimens to be used for exploratory research. Subjects who decline to participate in this optional research will indicate this in the ICF. If a subject withdraws consent to the use of donated biological samples, the samples will be disposed of/destroyed, and the action documented. If samples already have been analyzed at the time of the request, AstraZeneca will not be obliged to destroy the results of this research.

During the COVID-19 pandemic, re-consent may be obtained remotely and/or verbally if local/regional guidelines allow in order to reduce the risk of subjects of COVID-19 exposure during clinic visits. For further details please refer to [Appendix I](#).

A 4 Data protection

Each subject will be assigned a unique identifier by the sponsor. Any subject records or data sets transferred to the sponsor will contain only the identifier; subject names or any information which would make the subject identifiable will not be transferred.

The subject must be informed that his/her personal study-related data will be used by the sponsor in accordance with local data protection law. The level of disclosure must also be explained to the subject.

The subject must be informed that his/her medical records may be examined by Clinical Quality Assurance auditors or other authorized personnel appointed by the sponsor, by appropriate IRB/IEC members, and by inspectors from regulatory authorities.

A 5 Committees structure

The safety of all AstraZeneca clinical studies is closely monitored on an on-going basis by AstraZeneca representatives in consultation with Patient Safety. Issues identified will be addressed; for instance, this could involve amendments to the Clinical Study Protocol and letters to Investigators.

A 6 Dissemination of clinical study data

A description of this clinical trial will be available on <http://astrazenecaclinicaltrials.com> and <http://www.clinicaltrials.gov> as will the summary of the main study results when they are available. The clinical trial and/or summary of main study results may also be available on other websites according to the regulations of the countries in which the main study is conducted.

A 7 Data quality assurance

All subject data relating to the study will be recorded on printed or electronic CRF unless transmitted to the sponsor or designee electronically (eg, laboratory data). The investigator is responsible for verifying that data entries are accurate and correct by physically or electronically signing the CRF.

The investigator must maintain accurate documentation (source data) that supports the information entered in the CRF.

The investigator must permit study-related monitoring, audits, IRB/IEC review, and regulatory agency inspections and provide direct access to source data documents.

The sponsor or designee is responsible for the data management of this study including quality checking of the data.

Study monitors will perform ongoing source data verification to confirm that data entered into the CRF by authorized site personnel are accurate, complete, and verifiable from source documents; that the safety and rights of subjects are being protected; and that the study is being conducted in accordance with the currently approved protocol and any other study agreements, ICH GCP, and all applicable regulatory requirements.

Records and documents, including signed ICFs, pertaining to the conduct of this study must be retained by the investigator for 15 years after study completion unless local regulations or institutional policies require a longer retention period. No records may be destroyed during the retention period without the written approval of the sponsor. No records may be transferred to another location or party without written notification to the sponsor.

A 8 Source documents

Source documents provide evidence for the existence of the subject and substantiate the integrity of the data collected. Source documents are filed at the investigator's site.

Data reported on the CRF that are transcribed from source documents must be consistent with the source documents or the discrepancies must be explained. The investigator may need to request previous medical records or transfer records, depending on the study. Also, current medical records must be available.

Definitions of what constitutes source data can be found in the monitoring plan.

A 9 Publication policy

The results of this study may be published or presented at scientific meetings. If this is foreseen, the investigator agrees to submit all manuscripts or abstracts to the sponsor before submission. This allows the sponsor to protect proprietary information and to provide comments.

The sponsor will comply with the requirements for publication of study results. In accordance with standard editorial and ethical practice, the sponsor will generally support publication of multicentre studies only in their entirety and not as individual site data. In this case, a coordinating investigator will be designated by mutual agreement.

Authorship will be determined by mutual agreement and in line with International Committee of Medical Journal Editors authorship requirements.

Appendix B Adverse event definitions and additional safety information

B 1 Definition of adverse events

An adverse event is the development of any untoward medical occurrence in a subject or clinical study subject administered a medicinal product and which does not necessarily have a causal relationship with this treatment. An AE can therefore be any unfavourable and unintended sign (e.g. an abnormal laboratory finding), symptom (for example nausea, chest pain), or disease temporally associated with the use of a medicinal product, whether or not considered related to the medicinal product.

The term AE is used to include both serious and non-serious AEs and can include a deterioration of a pre-existing medical occurrence. An AE may occur at any time, including run-in or washout periods, even if no Study treatment has been administered.

B 2 Definitions of serious adverse event

A serious adverse event is an AE occurring during any study phase (i.e., run-in, treatment, washout, follow-up), that fulfils one or more of the following criteria:

- Results in death
- Is immediately life-threatening
- Requires in-subject hospitalisation or prolongation of existing hospitalisation
- Results in persistent or significant disability or incapacity.
- Is a congenital abnormality or birth defect
- Is an important medical event that may jeopardise the subject or may require medical treatment to prevent one of the outcomes listed above.

B 3 Life threatening

‘Life-threatening’ means that the subject was at immediate risk of death from the AE as it occurred or it is suspected that use or continued use of the product would result in the subject’s death. ‘Life-threatening’ does not mean that had an AE occurred in a more severe form it might have caused death (e.g., hepatitis that resolved without hepatic failure).

B 4 Hospitalisation

Outpatient treatment in an emergency room is not in itself a serious AE, although the reasons for it may be (e.g., bronchospasm, laryngeal oedema). Hospital admissions and/or surgical operations planned before or during a study are not considered AEs if the illness or disease existed before the subject was enrolled in the study, provided that it did not deteriorate in an unexpected way during the study.

B 5 Important medical event or medical treatment

Medical and scientific judgement should be exercised in deciding whether a case is serious in situations where important medical events may not be immediately life threatening or result in death, hospitalisation, disability or incapacity but may jeopardize the subject or may require medical treatment to prevent one or more outcomes listed in the definition of serious. These should usually be considered as serious.

Simply stopping the suspect drug does not mean that it is an important medical event; medical judgement must be used. Examples of such events are:

- Angioedema not severe enough to require intubation but requiring iv hydrocortisone treatment
- Hepatotoxicity caused by paracetamol (acetaminophen) overdose requiring treatment with N-acetylcysteine
- Intensive treatment in an emergency room or at home for allergic bronchospasm
- Blood dyscrasias (e.g., neutropenia or anaemia requiring blood transfusion, etc.) or convulsions that do not result in hospitalisation
- Development of drug dependency or drug abuse

B 6 Intensity rating scale:

1. mild (awareness of sign or symptom, but easily tolerated)
4. moderate (discomfort sufficient to cause interference with normal activities)
5. severe (incapacitating, with inability to perform normal activities)

It is important to distinguish between serious and severe AEs. Severity is a measure of intensity whereas seriousness is defined by the criteria in Appendix B 2. An AE of severe intensity need not necessarily be considered serious. For example, nausea that persists for several hours may be considered severe nausea, but not a SAE unless it meets the criteria shown in Appendix B 2. On the other hand, a stroke that results in only a limited degree of disability may be considered a mild stroke but would be a SAE when it satisfies the criteria shown in Appendix B 2.

B 7 A Guide to Interpreting the Causality Question

When making an assessment of causality consider the following factors when deciding if there is a 'reasonable possibility' that an AE may have been caused by the drug.

- Time Course. Exposure to suspect drug. Has the subject actually received the suspect drug? Did the AE occur in a reasonable temporal relationship to the administration of the suspect drug?

- Consistency with known drug profile. Was the AE consistent with the previous knowledge of the suspect drug (pharmacology and toxicology) or drugs of the same pharmacological class? Or could the AE be anticipated from its pharmacological properties?
- De-challenge experience. Did the AE resolve or improve on stopping or reducing the dose of the suspect drug?
- No alternative cause. The AE cannot be reasonably explained by another aetiology such as the underlying disease, other drugs, other host or environmental factors.
- Re-challenge experience. Did the AE reoccur if the suspected drug was reintroduced after having been stopped? AstraZeneca would not normally recommend or support a re-challenge.
- Laboratory tests. A specific laboratory investigation (if performed) has confirmed the relationship.

In difficult cases, other factors could be considered such as:

- Is this a recognized feature of overdose of the drug?
- Is there a known mechanism?

Causality of ‘related’ is made if following a review of the relevant data, there is evidence for a ‘reasonable possibility’ of a causal relationship for the individual case. The expression ‘reasonable possibility’ of a causal relationship is meant to convey, in general, that there are facts (evidence) or arguments to suggest a causal relationship.

The causality assessment is performed based on the available data including enough information to make an informed judgment. With limited or insufficient information in the case, it is likely that the event(s) will be assessed as ‘not related’.

Causal relationship in cases where the disease under study has deteriorated due to lack of effect should be classified as no reasonable possibility.

B 8 Medication Error

For the purposes of this clinical study a medication error is an unintended failure or mistake in the treatment process for an AstraZeneca study drug that either causes harm to the participant or has the potential to cause harm to the participant.

A medication error is not lack of efficacy of the drug, but rather a human or process related failure while the drug is in control of the study site staff or participant.

Medication error includes situations where an error.

- occurred

- was identified and intercepted before the participant received the drug
- did not occur, but circumstances were recognized that could have led to an error

Examples of events to be reported in clinical studies as medication errors:

- Drug name confusion
- Dispensing error e.g. medication prepared incorrectly, even if it was not actually given to the participant
- Drug not administered as indicated, for example, wrong route or wrong site of administration
- Drug not taken as indicated e.g. tablet dissolved in water when it should be taken as a solid tablet
- Drug not stored as instructed e.g. kept in the fridge when it should be at room temperature
- Wrong participant received the medication (excluding IVRS/IWRS errors)
- Wrong drug administered to participant (excluding IVRS/IWRS errors)

Examples of events that **do not** require reporting as medication errors in clinical studies:

- Errors related to or resulting from IVRS/IWRS - including those which lead to one of the above listed events that would otherwise have been a medication error
- Participant accidentally missed drug dose(s) e.g. forgot to take medication
- Accidental overdose (will be captured as an overdose)
- Participant failed to return unused medication or empty packaging
- Errors related to background and rescue medication, or standard of care medication in open label studies, even if an AZ product

Medication errors are not regarded as AEs but AEs may occur as a consequence of the medication error.

Appendix C Handling of Human Biological Samples

C 1 Chain of custody of biological samples

A full chain of custody is maintained for all samples throughout their lifecycle.

The Principal Investigator keeps full traceability of collected biological samples from the subjects while in storage at the centre until shipment or disposal (where appropriate).

The sample receiver keeps full traceability of the samples while in storage and during use until used or disposed of or until further shipment and keeps documentation of receipt of arrival.

AstraZeneca will keep oversight of the entire life cycle through internal procedures, monitoring of study sites, auditing or process checks, and contractual requirements of external laboratory providers

Samples retained for further use will be stored in the AZ-assigned biobanks and will be registered by the AstraZeneca Biobank Team during the entire life cycle.

If required, AstraZeneca will ensure that remaining biological samples are returned to the site according to local regulations or at the end of the retention period, whichever is the sooner.

C 2 Withdrawal of Informed Consent for donated biological samples

If a subject withdraws consent to the use of donated biological samples, the samples will be disposed of/destroyed, and the action documented. If samples are already analyzed, AstraZeneca is not obliged to destroy the results of this research.

As collection of the biological sample(s) is an integral part of the study, then the subject is withdrawn from further study participation.

The Investigator:

- Ensures subjects' withdrawal of informed consent to the use of donated samples is notified immediately to AstraZeneca
- Ensures that biological samples from that subject, if stored at the study site, are immediately identified, disposed of /destroyed, and the action documented
- Ensures the organization(s) holding the samples is/are informed about the withdrawn consent immediately and that samples are disposed of/destroyed, the action documented and the signed document returned to the study site
- Ensures that the subject and AstraZeneca are informed about the sample disposal.

AstraZeneca ensures the organizations holding the samples is/are informed about the withdrawn consent immediately and that samples are disposed of/destroyed and the action documented and returned to the study site.

C 3 International Airline Transportation Association (IATA) 6.2 Guidance Document

LABELLING AND SHIPMENT OF BIOHAZARD SAMPLES

International Airline Transportation Association (IATA) classifies biohazardous agents into 3 categories

(http://www.iata.org/whatwedo/cargo/dangerous_goods/infectious_substances.htm). For transport purposes the classification of infectious substances according to risk groups was removed from the Dangerous Goods Regulations in the 46th edition (2005). Infectious substances are now classified either as Category A, Category B or Exempt. There is no direct relationship between Risk Groups and Categories A and B.

Category A Infectious Substances are infectious substances in a form that, when exposure to it occurs, is capable of causing permanent disability, life-threatening or fatal disease in otherwise healthy humans or animals. Category A pathogens are e.g., Ebola, Lassa fever virus:

- are to be packed and shipped in accordance with IATA Instruction 602.

Category B Infectious Substances are infectious Substances that do not meet the criteria for inclusion in Category A. Category B pathogens are e.g., Hepatitis A, B, C, D, and E viruses, Human immunodeficiency virus types 1 and 2. They are assigned the following UN number and proper shipping name:

- UN 3373 – Biological Substance, Category B
- are to be packed in accordance with UN3373 and IATA 650

Exempt - all other materials with minimal risk of containing pathogens

- Clinical trial samples will fall into Category B or exempt under IATA regulations
- Clinical trial samples will routinely be packed and transported at ambient
- temperature in IATA 650 compliant packaging
(http://www.iata.org/whatwedo/cargo/dangerous_goods/infectious_substances.htm)
- **Biological samples transported in dry ice require additional dangerous goods specification for the dry-ice content**

- IATA compliant courier and packaging materials should be used for packing and transportation and packing should be done by an IATA certified person, as applicable
- Samples routinely transported by road or rail are subject to local regulations which require that they are also packed and transported in a safe and appropriate way to contain any risk of infection or contamination by using approved couriers and packaging/containment materials at all times. The IATA 650 biological sample containment standards are encouraged wherever possible when road or rail transport is used.

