7.3 Withdrawal from the study

A subject may withdraw from the study (e.g., withdraw consent), at any time (IP and assessments) at his/her own request, without prejudice to further treatment. A subject who considers withdrawing from the study must be informed by the Investigator about modified follow-up options (e.g., telephone contacts, contacts with a relative or treating physician, or information from medical records) as per section 7.1.1.

A subject who withdraws consent will always be asked about the reason(s) and the presence of any adverse events (AE). The Investigator will follow-up subjects as medically indicated. A withdrawal visit is essential to collect as much data as possible for the subject as per EOT visit described in SoA, Table 2. The subject will return all study supplied equipment including Home PEF meter and eDiary.

If the subject withdraws consent for disclosure of future information, the sponsor may retain and continue to use any data collected before such a withdrawal of consent.

If a subject withdraws from the study, he/she may request destruction of any samples taken, and the investigator must document this in the site study records.

If the subject only withdraws consent for the retention of blood samples for future exploratory use (e.g., DNA, study of markers of asthma, identifying potential new drug targets for asthma, or for assay development purposes), the subject will not be withdrawn from the study.

Withdrawal of consent from the study must be ascertained and documented by the Investigator and recorded in the eCRF as well as in the Informed Consent Form (ICF) or assent form.

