9.4.3 Efficacy analysis

9.4.3.1 Analysis of the primary efficacy endpoint

The primary analysis of the primary efficacy endpoint (AAER over 52 weeks) will quantify the effect of the initially randomized treatment, regardless of the treatments that subjects actually received, or whether the subjects received other controller therapy/rescue medications post IP discontinuation. This analysis will therefore include all available data after treatment discontinuation. Subjects will be encouraged to continue to undergo applicable study related visits/procedures for the full 52-week period even after premature discontinuation of IP. Consequently, subjects lost to follow-up and subjects who withdraw their consent will be the only source of missing information for the primary analysis. Missing data from study discontinuation will be modelled based on what was observed during the study using direct likelihood approaches, which is a valid approach under the assumption that data are missing at random (MAR).

AAER in the tezepelumab group will be compared to that seen in the placebo group using a negative binomial model. This model will be used to perform the statistical test specified in Section 9.1, and to estimate the treatment effect and both its 99% and 95% confidence intervals. The response variable in the model will be the number of asthma exacerbations experienced by a subject over the 52-week study period (or shorter duration if not followed up for the full 52 weeks). Treatment, region, age (adolescents or adults) and history of exacerbations (2 or >2 in previous 12 months) will be included as factors in this model. The logarithm of the time at risk for exacerbation in the study will be used as an offset variable in the model, to adjust for subjects having different follow-up times during which the events occur. Time during an exacerbation and the 7 days following an exacerbation in which a new exacerbation cannot occur, will not be included in the calculation of time at risk for exacerbation.

Descriptive summaries of the asthma exacerbations will also be presented.

Annualized rates for the individual exacerbation criteria (emergency room or urgent care visits due to asthma that required systemic corticosteroids, hospitalization due to asthma, or use of

systemic corticosteroids) will be summarized descriptively and analyzed using a similar model as for the primary endpoint.

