- Non-leukocyte depleted whole blood transfusion in 120 days of genetic sample collection

Withdrawal of consent for genetic research:

Subjects may withdraw from this genetic research at any time, independent of any decision concerning participation in other aspects of the main study. Voluntary withdrawal will not prejudice further treatment. Procedures for withdrawal are outlined in Section 7.3 of the main Clinical Study Protocol.

Collection of samples for genetic research

Blood samples for genetic research will be obtained from subjects at Visit 3, 10, 17 and 19. Although DNA is stable, early sample collection is preferred to avoid introducing bias through excluding subjects who may withdraw due to an adverse event (AE), such subjects would be important to include in any genetic analysis. Samples will be collected, labelled, stored, and shipped as detailed in the Laboratory Manual.

Coding and storage of DNA samples

The processes adopted for the coding and storage of samples for genetic analysis are important to maintain subject confidentiality. Samples will be stored for a maximum of 15 years, from the date of last subject last visit, after which they will be destroyed. DNA is a finite resource that is used up during analyses. Samples will be stored and used until no further analyses are possible or the maximum storage time has been reached.

An additional second code will be assigned to the blood either before or at the time of DNA extraction replacing the information on the sample tube. Thereafter, the sample will be identifiable only by the second, unique number. This number is used to identify the sample and corresponding data at the AstraZeneca genetics laboratories, or at the designated organisation. No personal details identifying the individual will be available to any person (AstraZeneca employee or designated organisations working with the DNA).

The link between the subject enrolment/randomization code and the second number will be maintained and stored in a secure environment, with restricted access at AstraZeneca or designated organisations. The link will be used to identify the relevant DNA samples for analysis, facilitate correlation of genotypic results with clinical data, allow regulatory audit, and permit tracing of samples for destruction in the case of withdrawal of consent.

Ethical and regulatory requirements

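### Appendix C 2 withdraws a subject from the trial for any withdrawal of consent to sample use, contradicting Section 7.3 and Appendix D 2 for optional exploratory and genetic samples

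*Protocol*

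**What the plan says.** Four places in the protocol deal with a subject who changes their mind about samples.

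- **Appendix C 2** opens with withdrawal of consent to the use of donated biological samples, with no restriction on the kind of sample. The samples are destroyed. Then: "As collection of the biological sample(s) is an integral part of the study, then the subject is withdrawn from further study participation".
- **Section 7.3** covers a narrower case: "If the subject only withdraws consent for the retention of blood samples for future exploratory use". Its examples include DNA, asthma markers, drug targets and assay development. The consequence is that "the subject will not be withdrawn from the study".
- **Appendix A 3**, in its paragraph on optional exploratory use of leftover mandatory samples, tells subjects that "they are free to refuse to participate and may withdraw their consent at any time and for any reason during the storage period". It continues: "If a subject withdraws consent to the use of donated biological samples, the samples will be disposed of/destroyed, and the action documented". This is the sentence that opens C 2, but no study withdrawal follows. Separately, for a subject who declines genetic research, it says "he/she will not be excluded from other aspects of the study".
- **Appendix D 2** says: "Subjects may withdraw from this genetic research at any time, independent of any decision concerning participation in other aspects of the main study". It sends the reader to Section 7.3 for the procedure.

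On the analysis side, Section 9.4.3.1 states that "subjects lost to follow-up and subjects who withdraw their consent will be the only source of missing information for the primary analysis". SAP Section 4.2.4.1 repeats this and adds death.

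**The concern.** C 2 is where the protocol tells the investigator what to do when a subject withdraws sample consent, so it is a natural place for a site to look. Read as written, it takes a subject out of the trial because they asked for a stored DNA or exploratory sample to be destroyed. Section 7.3 gives the opposite instruction for the same request. With about 400 sites planned (Synopsis), different handling is foreseeable.

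Two things are at stake. The primary analysis follows a treatment policy strategy and uses all data to Week 52, so each needless withdrawal removes exacerbation follow-up that could have been collected, as well as the Week 52 key secondary values. Deriving an exacerbation (Section 8.1.1; SAP Section 3.2.1.1) needs no blood sample. The second matter is consent. Appendix D presents the genetic research as something a subject may leave without effect on the main study, and C 2 would make leaving it cost the subject their place in the trial.

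**Working it through.** **Step 1. Compare the rules.**

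| Place | Trigger | Samples covered | Effect on participation |
|---|---|---|---|
| C 2 | Consent to sample use withdrawn | Any | Removed from the study |
| 7.3 | Only consent to exploratory retention withdrawn | Exploratory, DNA included | Stays |
| A 3 | Same sentence as C 2 | Leftover samples in optional research | None stated |
| D 2 | Leaves genetic research | Genetic | Independent of main study |

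**Step 2. Apply them to three requests.**

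1. *An adult asks for stored DNA to be destroyed.* C 2 removes the subject; 7.3 and D 2 keep the subject in. This is a direct contradiction. The reason C 2 gives, that collection is integral to the trial, is untrue here because Section 8.7.1 makes the DNA sample optional.
2. *A subject withdraws agreement to exploratory use of leftover serum.* C 2 removes the subject; 7.3 keeps the subject in. This is a direct contradiction. A 3 attaches no removal.
3. *A subject withdraws consent to mandatory safety, PK or ADA samples.* C 2 removes the subject. Sections 7.3, A 3 and D 2 do not address this case, so there is no contradiction.

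**Step 3. Cost per affected subject.** Withdrawal at mid-year loses 26/52 = 0.5 year of exacerbation follow-up. At the planning rates in Section 9.2 that is 0.9 × 0.5 = 0.45 expected events on placebo and 0.45 × 0.5 = 0.225 on tezepelumab. SAP Table 7 also matters. In the dropout-reason imputation, a tezepelumab subject who stopped treatment by own decision or for another reason is imputed from placebo by default, unless blinded review of recorded comments clearly shows a cause unrelated to treatment.

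**Step 4. Does power depend on this?** Inputs from Section 9.2 are 530 per arm, placebo rate r0 = 0.9, a 50% reduction (r1 = 0.45), shape k = 2.4, 10% uniform dropout and two-sided alpha 0.01. Mean follow-up is μ = 1 − d/2 = 0.95 year, where d is the dropout proportion. In the Wald form of the negative binomial comparison:

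V = (1/μ)(1/r0 + 1/r1) + 2k = 3.333/0.95 + 4.8 = 8.309

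z = √530 × ln 2 / √8.309 − 2.576 = 5.536 − 2.576 = 2.960, giving power 0.9985

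This reproduces the plan's figure of more than 99%. For the low-eosinophil subgroup (265 per arm, r0 = 0.6, r1 = 0.3, alpha 0.05), V = 5/0.95 + 4.8 = 10.063 and power is 0.945, against 94% stated.

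Raising total dropout, as an assumed range:

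| Dropout | Primary | Subgroup |
|---|---|---|
| 10% | 0.9985 | 0.945 |
| 11% | 0.9984 | 0.944 |
| 15% | 0.9983 | 0.942 |
| 20% | 0.9981 | 0.939 |

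Even doubling dropout costs less than one percentage point in either test.

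**The case against.** The best defence is that the protocol already settles the optional-sample case. Section 7.3 sits in the body and states the specific exception, D 2 points to it, and the word integral in C 2 suggests that only mandatory samples were meant. A careful site would probably reach the right answer, at least for genetic samples. Part of this stands: it lowers the likely number of events and shows what the sponsor probably intended. It does not remove the contradiction. C 2 never states that scope and has no cross-reference to 7.3. It shares its opening sentence with the optional-research paragraph of A 3, and its remark about results already obtained closely follows that paragraph too.

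It is also fair that the loss may be limited. Section 7.3 asks for a withdrawal visit and discussion of modified follow-up, and the SAP has dropout-reason and tipping-point sensitivity analyses. Samples may be stored for up to 15 years after the last subject's last visit, so some requests will come after participation has ended and cost no trial data.

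A reader might infer more than the documents support:

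- *That C 2 is wrong for mandatory samples too, because Section 7.1.1 Options 2 and 3 follow subjects with little sampling.* Those options apply only after treatment has been discontinued. The discontinuation visit and Visit 19 still carry chemistry, haematology, PK and ADA samples in Table 2. They do not show that a subject can continue in the trial without mandatory samples.
- *That A 3 promises no exclusion after a later withdrawal of sample consent.* Its explicit assurance concerns declining genetic research. For later withdrawal it simply attaches no study withdrawal.
- *That a head count of lost subjects can be given.* No document states a rate of sample-consent withdrawal.

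**Conclusion.** The point holds for optional exploratory and genetic samples, and C 2 is wrong as written. It states a rule which, if followed, removes subjects whom Section 7.3 and D 2 keep in, and it does not fit A 3. It is more than a missing detail, because it decides who stays under observation for the primary endpoint.

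The size is modest. The number affected cannot be estimated and is probably small, and the power calculation does not materially depend on it. That check assumes the Section 9.2 planning values and uniform dropout. The harm is avoidable missing data under the treatment policy strategy, inconsistent handling between sites, and a conflict with what Appendix D tells subjects about voluntary research. The conclusion does not extend to mandatory samples.

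**What to change.** Reconcile C 2 with Sections 7.3, A 3 and D 2. Limit its study-withdrawal sentence to mandatory study samples, and add wording such as: withdrawal of consent for optional exploratory or genetic samples, including exploratory use of material left over from mandatory samples, is handled under Section 7.3 and does not by itself withdraw the subject from the study. Leftover material needs naming because A 3 concerns optional research on the remains of mandatory samples, so a limit defined only by type of sample could leave the ambiguity in place.

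A sentence keeping subjects in after withdrawal of consent to any sample would go too far. It would reach the safety laboratory samples on which the liver-related discontinuation criteria in Section 7.1 and the Appendix E review depend. What happens when consent to mandatory samples is withdrawn is left as the sponsor has it.

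The cost is one qualified sentence and one cross-reference in an appendix. No hypothesis, sample size, analysis or SAP text changes, and the optional samples concerned would be destroyed under either rule.
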